#### Follow-up of AE/SAE/Device Deficiency

- The investigator is obligated to perform or arrange for the conduct of supplemental
  measurements and/or evaluations as medically indicated or as requested by the
  sponsor to elucidate the nature and/or causality of the AE/SAE/device deficiency as
  fully as possible. This may include additional laboratory tests or investigations,
  histopathological examinations, or consultation with other healthcare providers.
- If a participant dies during participation in the study or during a recognized followup period, the investigator will provide Pfizer Safety with a copy of any postmortem findings including histopathology.

- New or updated information will be recorded in the originally completed CRF.
- The investigator will submit any updated SAE data to the sponsor within 24 hours of receipt of the information.

#### 10.8.5. Reporting of SAEs

## SAE Reporting to Pfizer Safety via CT SAE Report Form

- Facsimile transmission of the CT SAE Report Form is the preferred method to transmit this information to Pfizer Safety.
- In circumstances when the facsimile is not working, notification by telephone is acceptable with a copy of the CT SAE Report Form sent by overnight mail or courier service.
- Initial notification via telephone does not replace the need for the investigator to complete and sign the CT SAE Report Form pages within the designated reporting time frames.

### 10.8.6. Reporting of SADEs

## **SADE Reporting to Pfizer Safety**

NOTE: There are additional reporting obligations for medical device incidents that are potentially related to SAEs that must fulfill the legal responsibility to notify appropriate regulatory authorities and other entities about certain safety information relating to medical devices being used in clinical studies.

- Any device deficiency that is associated with an SAE must be reported to the sponsor within 24 hours after the investigator determines that the event meets the definition of a device deficiency.
- The sponsor shall review all device deficiencies and determine and document in writing whether they could have led to an SAE. These shall be reported to the regulatory authorities and IRBs/ECs as required by national regulations.

## 10.9. Appendix 9: Abbreviations

The following is a list of abbreviations that may be used in the protocol.

Abbreviation	Term
ABR	annualized bleeding rate
Abs	Absolute
ADA	antidrug antibodies
ADCC	antibody-dependent cell-mediated cytotoxicity
ADE	adverse device effect
AE	adverse event
ALB	albumin
ALT	alanine aminotransferase
aPCC	activated prothrombin complex concentrate
APTT	activated partial thromboplastin time
AST	aspartate aminotransferase
ATIII	anti-thrombin III
AUC	area under the curve
AUCinf	area under the concentration time curve from time 0 to infinity
AUC last	area under the concentration time curve from time 0 to the time of
	the last quantifiable concentration
AUCt	area under the concentration-time curve from time 0 to time t, where
	t can have a numerical value
AUEC	area under the PD change from baseline time profile from time zero
	to Day 28
BID	Twice a day
BP	blood pressure
bpm	beats per minute
BUN	blood urea nitrogen
CDC	Complement dependent cytotoxicity
CDE	Center for Drug Evaluation
CFR	Code of Federal Regulations
CIOMS	Council for International Organizations of Medical Sciences
CK	creatine kinase
Cmax	maximum observed concentration
CNS	central nervous systems
CL/F	apparent clearance
CO 2	carbon dioxide (bicarbonate)
CONSORT	Consolidated Standards of Reporting Trials
COVID-19	Coronavirus Disease 2019
CRF	case report form
CRO	contract research organization
CRU	clinical research unit
CSR	clinical study report
CT	clinical trial

Abbreviation	Term
CTCAE	Common Terminology Criteria for Adverse Events
cTnI	cardiac troponin I
CV	cardiovascular
%CV	geometric percent coefficient of variation
DILI	drug induced liver injury
DMC	data monitoring committee
dPT	dilute prothrombin time
DRE	disease-related event
EC	ethics committee
ECG	Electrocardiogram
eCRF	electronic case report form
EDP	exposure during pregnancy
EMA	European Medicines Agency
EU	European Union
EudraCT	European Clinical Trials Database
FcR	Fc receptor
Fg	fibrinogen
FIH	first in human
FIP	first in patient
FVIIa	factor-activated coagulation factor VII
FIX	coagulation factor IX
FXa	activated coagulation factor IX
rFVIIa	recombinant activated coagulation factor VII
FVIII	coagulation factor VIII
GCP	Good Clinical Practice
eGFR	Estimated glomerular filtration rate
GGT	gamma-glutamyl transferase
GLOB	globulin
GLP	Good Laboratory Practice
HbcAb	hepatitis B core antibody
HbsAg	hepatitis B surface antigen
HCVAb	hepatitis C antibody
HIPAA	Health Insurance Portability and Accountability Act
HIV	human immunodeficiency virus
Kel	the terminal phase rate constant calculated by a linear regression of
	the loglinear concentration time curve.
K1	Kunitz domain 1
K2	Kunitz domain 2
hr	hours
IB	investigator's brochure
ICD	informed consent document
ICH	International Council for Harmonisation
ID	Identification

Abbreviation	Term
IFN- γ	Interferon gamma
IgG1	immunoglobulin G isotype, subclass 1
IMP	investigational medicinal product
IND	investigational new drug application
INR	international normalized ratio
IL-6	Interleukin-6
IP manual	investigational product manual
ISO	International Organization for Standardization
IRB	institutional review board
IV	intravenous
IVIG	IV immunoglobulin
LFT	liver function test
LLN	lower limit of normal
Max Eff	Maximum PD change from baseline
MCH	mean corpuscular hemoglobin
MCHC	mean corpuscular hemoglobin concentration
MCV	mean corpuscular volume
min	minutes
msec	millisecond
N/A	not applicable
NAb	neutralizing antibodies
NIMP	noninvestigational medicinal product
NMPA	National Medical Products Administration
NOAEL	no-observed-adverse-effect level
NSAIDs	non-steroidal anti-inflammatory drugs
PCC	prothrombin complex concentrate
PCD	primary completion date
PD	pharmacodynamic(s)
PF1+2	prothrombin fragment 1+2
PK	pharmacokinetic(s)
PT	prothrombin time
PWH	people with hemophilia
PVC	premature ventricular contraction/complex
QW	once weekly
QTc	corrected QT interval
QTcF	corrected QT interval (Fridericia method)
QoL	quality of life
QW	once weekly
RBC	red blood cell
RNA	ribonucleic acid
SADE	serious adverse device effect
SAE	serious adverse event
SAP	statistical analysis plan

Abbreviation	Term
SARS-CoV2	severe acute respiratory syndrome coronavirus 2
SC	subcutaneous
SoA	schedule of activities
SOP	standard operating procedure
SPR	Surface Plasmon Resonance
SRSD	single reference safety document
SUSAR	suspected unexpected serious adverse reaction
t 1/2	apparent terminal half-life
Tbili	total bilirubin
TCMs	traditional Chinese medicine
TEAE	treatment-emergent adverse events
TEG	thromboelastography
TF	tissue factor
TGA	thrombin generation assays
THC	tetrahydrocannabinol
TFPI	tissue factor pathway inhibitor
$T_{\text{max}}$	time to reach maximum concentration
TNF a	Tumor necrosis factor a
TK	toxicokinetic
ULN	upper limit of normal
US	United States
WBC	white blood cell
WFH	World Federation of Hemophilia

## 10.10. Appendix 10: Alternative Measures During Public Emergencies

The alternative study measures described in this section are to be followed during public emergencies, including the COVID-19 pandemic. This appendix applies for the duration of the COVID-19 pandemic globally and will become effective for other public emergencies only upon written notification from Pfizer.

Use of these alternative study measures are expected to cease upon the return of business as usual circumstances (including the lifting of any quarantines and travel bans/advisories).

## **10.10.1.** Eligibility

While SARSCoV2 testing is not mandated for this study, local clinical practice standards for testing should be followed. A patient should be excluded if he/she has a positive test result for SARS-CoV2 infection, is known to have asymptomatic infection, or is suspected of having SARS-CoV2.

#### 10.10.2. Telehealth Visits

In the event that in-clinic study visits can not be conducted, every effort should be made to follow- up on the safety of study participants at scheduled visits per the Schedule of Activities or unscheduled visits. Telehealth visits may be used to continue to assess participant safety and collect data points. Telehealth includes the exchange of healthcare information and services via telecommunication technologies (e.g., audio, video, video-conferencing software) remotely, allowing the participant and the investigator to communicate on aspects of clinical care, including medical advice, reminders, education, and safety monitoring. The following assessments must be performed during a telehealth visit:

- Review and record any new concomitant medications or changes in concomitant medications since last contact.
- Review and record any AEs and SAEs since last contact, including but not limited to COVID-19 related events. The AE and SAE reporting process should be followed per protocol (Section 10.3, Appendix 3).
- Confirm that the participant is adhering to the contraception method(s) required in the protocol.
- Review bleeding episodes and factor or bypass infusions.

Study participants must be reminded to promptly notify site staff about any change in their health status.

## 10.10.3. Alternative Facilities for Safety Assessments

## 10.10.3.1. Laboratory Testing

If a study participant is unable to visit the site for protocol-specified safety laboratory evaluations, testing may be conducted at a local laboratory if permitted by local regulations. The local laboratory may be a standalone institution or within a hospital. The following safety laboratory evaluations may be performed at a local laboratory:

- Hematology
- Serum chemistry
- APTT,PT/INR,Fg
- Anti-thrombin III;
- Cardiac Troponin I;
- Urinalysis;

If a local laboratory is used, qualified study site personnel must order, receive, and review results. Site staff must collect the local laboratory reference ranges and certifications/ accreditations for filing at the site. Laboratory test results are to be provided to the site staff as soon as possible. The local laboratory reports should be filed in the participant's source documents/medical records. Relevant data from the local laboratory report should be recorded on the CRF.

## 10.10.3.2. Electrocardiograms

If the participant is unable to visit the study site for ECGs, the participant may visit an alternative facility to have the ECGs performed. Qualified study site personnel must order, receive, and review results.

## 10.10.4. Study Intervention

If the safety of a trial participant is at risk because they cannot complete required evaluations or adhere to critical mitigation steps, then discontinuing that participant from study intervention must be considered.

#### 10.10.5. Home Health Visits

A home health care service may be utilized to facilitate scheduled visits per the Schedule of Activities. Home health visits include a healthcare provider conducting an in-person study visit at the participant's location, rather than an in-person study visit at the site. The following may be performed during a home health visit:

- Physical exam/brief physical exam
- All protocol required lab draws
- Weight and vital signs (eg, body temperature, BP, pulse rate, respiratory rate).

## 10.10.6. Adverse Events and Serious Adverse Events

If a participant has COVID-19 during the study, this should be reported as an adverse event (AE) or serious adverse events (SAE) and appropriate medical intervention provided. It is recommended that the investigator discuss temporary or permanent discontinuation of study intervention with the study medical monitor.

1. VERSION HISTORY

 Table 1.
 Summary of Changes

Version/ Date	Associated Protocol Amendment	Rationale	Specific Changes
1	Original	N/A	N/A
19 Dec 2019	24 Oct 2019		
2 20 May 2021	Amendment 1 22-Oct-2020	Update according to Protocol Amendment 1; Clarification of prior version.	• Primary Endpoint: Frequency, severity and causal relationship of treatment emergent adverse events (TEAEs) and withdrawals due to TEAE; Day 1 up to Day 28 42. (Section 2.1, Section 3.1)
			• Changed "one way" to "single-arm". (Header, Section2.2)
			• Added clarification that tissue factor pathway inhibitor (TFPI) samples were for both total and free TFPI. (Section 2.1, Section 3.2.2, Section 3.4, Section 6.2.2)
			Added: The follow-up Visit at Day 42 could be a Phone Follow-Up visit or a face to face clinic visit at the discretion of the investigator. If Day 42 visit and the Screening visit of B7841005 occur on the same day, it must be a clinic visit. (Section 2.2)
			• The maximum total duration of the study for a single participant, from initial screening to final follow up, will be approximately 2 2.5 months. (Section 2.2)
			• Added clarification: Participants who complete Study B7841010 will be eligible to be enrolled in the global pivotal Phase 3 study, B7841005, unless a specific inclusion criterion is

not met or an exclusion criterion is noted before Day 1 (Screening visit), of B7841005. (Section 2.2)
• Added footnote to Table 3 to clarify that t _{1/2} , AUC _{inf} , CL/F and V _z /F will be reported if data permit.
• Added detailed list of baseline variables. (Section 3.4)
• Added description for "Physical Examination" in Safety Endpoints. (Section 3.5.5)
Added detailed reporting for ECG data, PT/INR, APTT, fibrinogen and ATIII activity. (Section 6.1)
Added detailed reporting for Max _{Eff} and AUEC with respect to PD endpoints. (Section 6.2.2)
Added subsections "Summary of Hemophilia History", "Summary of Bleeding Events" "Demographic and Clinical Examination Data", "Study Treatment Exposure" and "Concomitant Medications and Non- Drug Treatments" in Section 6.5.
Added Apendix 1: Categorical Classes for ECG and Vital Signs of Potential Clinical Concern; added Appendix 2: Clinically Laboratory, Vital Sign, and ECG Values.

2. INTRODUCTION

PF-06741086 is a human monoclonal immunoglobulin of the G isotype, subclass 1 (IgG1) that targets the Kunitz-2 domain of tissue factor pathway inhibitor (TFPI). PF-06741086 is in development as a prophylactic treatment to prevent or reduce the frequency of bleeding episodes in individuals with severe hemophilia A or B, with or without inhibitors.

This statistical analysis plan (SAP) provides the detailed methodology for summary and statistical analyses of the data collected in Study B7841010. This document may modify the

plans outlined in the protocol; however, any major modifications of the primary endpoint definition or its analysis will also be reflected in a protocol amendment.

2.1. Study Objectives, Endpoints, and Estimands

Table 2. Objectives and Endpoints

Objectives	Endpoints
Primary:	Primary:
To determine the safety and tolerability of a single subcutaneous (SC) dose of PF-06741086 administered to Chinese adult participants with severe hemophilia A or B, with or without inhibitors.	• Frequency, severity and causal relationship of treatment emergent adverse events (TEAEs) and withdrawals due to TEAE; Day 1 up to Day 42.
	• Frequency and magnitude of abnormal laboratory findings (including hematology, prothrombin time (PT)/international normalized ratio (INR), activated partial thromboplastin time (APTT), chemistry, urinalysis, fibrinogen, anti-thrombin III (ATIII) activity and cardiac troponin I (cTnI)); Day 1 up to Day 28.
	• Changes from baseline in vital sign (blood pressure, pulse rate, temperature and respiration rate) measurements, 12-lead electrocardiogram (ECG) parameters and physical examination; Day 1 up to Day 28.
	• Frequency, severity and causal relationship of injection site reactions; Day 1 up to Day 7.
Secondary:	Secondary:
To characterize the pharmacokinetic (PK) profile of a single SC dose of PF-06741086.	Plasma PF-06741086 concentrations as determined by a validated assay from Day 1 up to Day 28, and noncompartmental PK parameters including peak or maximum observed concentration (C _{max}), time to reach maximum concentration (T _{max}), area under the concentration-time curve from time 0 to the time of the last quantifiable concentration (AUC _{last}),

- To characterize the pharmacodynamic (PD) profile of a single SC dose of PF-06741086.
- To characterize the immunogenicity of a single SC dose of PF-06741086.

- area under the concentration-time curve from time 0 to infinity (AUC $_{inf}$), terminal half-life ($t_{1/2}$), apparent volume of distribution (V_z/F), apparent clearance (CL/F).
- TFPI (total and free); Thrombin generation (including lag time, peak thrombin generation and endogenous thrombin generation potential); Prothrombin fragment 1+2 (PF 1+2); D-dimer; Dilute prothrombin time (dPT); Day 1 up to Day 28.
- Frequency of anti-drug antibody (ADA) and neutralizing antibody (NAb) production against PF-06741086; Day 1 up to Day 28. Only positive ADA samples and the corresponding baseline sample will be tested in the NAb assay.

2.2. Study Design

This is a Phase 1, single-arm, open-label, non-randomized, non-controlled, multicenter, study in 6 Chinese adult participants between ages 18 to <75 years with severe hemophilia A or B (defined as coagulant Factor VIII (FVIII) or coagulant Factor IX (FIX) activity <1%, respectively), with or without inhibitor. This study aims to evaluate the PK, PD, safety and tolerability of a single SC dose of PF-06741086.

Approximately 6 participants are planned for enrollment at 2 study sites. Participants who are withdrawn for any reasons may be replaced at the discretion of the investigator and after consultation with the sponsor. Participants will be screened within 35 days prior to administration of the investigational product to confirm that they meet the participant selection criteria for the study. Participants will be admitted into the Clinical Research Unit (CRU) 1 day prior to dosing (Day-1) and will accept a single SC injection of 300 mg PF-06741086 (150 mg *2) at Day 1. There is no dose modification plan during the study. Participants will be required to stay in the CRU through completion of the Day 7 evaluations. After that, it will be at investigator's discretion on whether the participants should stay in the CRU or not. All participants will return for weekly clinic visits on Day 14, Day 21 and Day 28 per the Schedule of Activities. The follow-up Visit at Day 42 could be a Phone Follow-Up visit or a face to face clinic visit at the discretion of the investigator. If Day 42 visit and the Screening visit of B7841005 occur on the same day, it must be an in- clinic visit.

Participants who experience a treatment-related adverse event (including lab abnormalities) at any time point will continue to be followed through resolution or stabilization of the event as agreed upon by the investigator and sponsor.

The maximum total duration of the study for a single participant, from initial screening to final follow-up, will be approximately 2.5 months.

Participants who complete Study B7841010 will be eligible to be enrolled in the global pivotal Phase 3 study, B7841005, unless a specific inclusion criterion is not met or an exclusion criterion is noted before Day 1 (Screening visit), of B7841005.

3. ENDPOINTS AND BASELINE VARIABLES: DEFINITIONS AND CONVENTIONS

3.1. Primary Endpoints

- Frequency, severity and causal relationship of TEAEs and withdrawals due to TEAE; Day 1 up to Day 42.
- Frequency and magnitude of abnormal laboratory findings (including hematology, PT/INR, APTT, chemistry, urinalysis, fibrinogen, ATIII activity and cTnI); Day 1 up to Day 28.
- Changes from baseline in vital signs (blood pressure, pulse rate, temperature and respiration rate) measurements, 12-lead ECG parameters and physical examination; Day 1 up to Day 28.
- Frequency, severity and causal relationship of injection site reactions; Day 1 up to Day 7.

3.2. Secondary Endpoints

3.2.1. Pharmacokinetic Endpoints

Plasma PF-06741086 concentrations as determined by a validated assay Day 1 up to Day 28, and noncompartmental PK parameters including C_{max} , T_{max} , AUC_{last} , AUC_{inf} , $t_{1/2}$, V_z/F , CL/F.

PK parameters of PF-06741086 following single dose administration will be derived from the concentration-time profiles as shown in the table below.

Table 3. Derivation of PF-06741086 Pharmacokinetic Parameters

Parameter	Definition	Method of Determination
C _{max}	Maximum plasma concentration	Observed directly from data
T_{max}	Time for C _{max}	Observed directly from data as time of first occurrence
$\mathbf{t}_{\mathcal{V}_2}^{\mathbf{a}}$	Terminal half-life	Log _e (2)/k _{el} , where k _{el} is the terminal phase rate constant calculated by a linear regression of the log-linear concentration-time curve

AUC _{last}	Area under the plasma concentration-time profile from time zero to the time of the last quantifiable concentration (C_{last})	Linear/Log trapezoidal method
$\mathrm{AUC_{inf}}^a$	Area under the plasma concentration-time profile from time zero extrapolated to infinite time	AUC _{last} + (C _{last} /k _{el}), where C _{last} is the predicted plasma concentration at the last quantifiable time point estimated from the log-linear regression analysis
CL/F ^a	Apparent clearance	Dose/AUC _{inf}
V_z/F^a	Apparent volume of distribution	Dose/(AUCinf*kel)

a. If data permit.

Actual PK sampling times will be used in the derivation of PK parameters.

3.2.2. Pharmacodynamic Endpoints

TFPI (total and free, "free" TFPI will only be analyzed if this assay is validated before the study completes"); Thrombin generation (including lag time, peak thrombin generation and endogenous thrombin generation potential); PF 1+2; D-dimer; dPT; Day 1 up to Day 28.

3.2.3. Immunogenicity Endpoints

Frequency of ADA and NAb production against PF-06741086; Day 1 up to Day 28. Only positive ADA samples and the corresponding baseline sample will be tested in the NAb assay.

3.3. Other Endpoints

None.

3.4. Baseline Variables

Baseline variables include,

- Medical history;
- Prior/concomitant medication;
- Physical examination;
- Demographics;
- Height and weight;
- Clinical laboratory tests;

- Vital signs;
- ECG parameters;
- ADA and NAb;
- PK concentration;
- PD endpoints: TFPI (total and free), dPT, PF1+2, D-dimer, thrombin generation (including lag time, peak thrombin generation, and endogenous thrombin generation potential).

Baseline is defined as the last pre-dose measurement except for ECG data. Baseline for ECG data will be defined as the average of triplicate ECG measurements collected prior to dosing on Day 1.

3.5. Safety Endpoints

3.5.1. Adverse Events

An adverse event will be considered a Treatment-Emergent Adverse Event (TEAE) if the event started during the effective duration of treatment regardless of whether a similar event of equal or greater severity existed in the baseline period.

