## 8.3.1. Time Period and Frequency for Collecting AE and SAE Information

The time period for actively eliciting and collecting AEs and SAEs ("active collection period") for each participant begins from the time the participant provides informed consent, which is obtained before the participant's participation in the study (ie, before undergoing any study related procedure and/or receiving investigational product), through and including a minimum of 42 calendar days after the last administration of the study intervention.

Follow-up by the investigator continues throughout and after the active collection period and until the AE or SAE or its sequelae resolve or stabilize at a level acceptable to the investigator, and Pfizer concurs with that assessment.

For participants who are screen failures, the active collection period ends when screen failure status is determined.

If the participant withdraws from the study and also withdraws consent for the collection of future information, the active collection period ends when consent is withdrawn.

If a participant definitively discontinues or temporarily discontinues study intervention because of an AE or SAE, the AE or SAE must be recorded on the CRF and the SAE reported using the CT SAE Report Form.

Investigators are not obligated to actively seek AEs or SAEs after conclusion of the study participation. However, if the investigator learns of any SAE, including a death, at any time after a participant has been discharged from the study, and he/she considers the event to be reasonably related to the study intervention, the investigator must promptly report the SAE to Pfizer using the CT SAE Report Form..

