#### Follow-up of AEs and SAEs

- The investigator is obligated to perform or arrange for the conduct of supplemental
  measurements and/or evaluations as medically indicated or as requested by the sponsor
  to elucidate the nature and/or causality of the AE or SAE as fully as possible. This may
  include additional laboratory tests or investigations, histopathological examinations, or
  consultation with other healthcare professionals.
- If a participant dies during participation in the study or during a recognized follow-up period, the investigator will provide Pfizer Safety with a copy of any postmortem findings including histopathology.
- New or updated information will be recorded in the originally completed CRF.
- The investigator will submit any updated SAE data to the sponsor within 24 hours of receipt of the information.

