6. ANALYSES AND SUMMARIES

6.1. Primary Endpoints (Safety Analyses)

All safety analyses will be performed on the safety population (as defined in Section 4).

Analysis of frequency, severity and causal relationship of AEs, TEAEs from Day 1 up to Day 42, and injection site reactions from Day 1 up to Day 7 will be provided. Changes from baseline in vital sign (blood pressure (BP), pulse rate, temperature and respiration rate) measurements and ECG parameters from Day 1 up to Day 28 will be summarized. Physical examination findings from Day 1 up to Day 28 will be listed. Frequency and magnitude of abnormal laboratory findings (including hematology, PT/INR, APTT, chemistry, urinalysis, fibrinogen, ATIII activity, and cTnI), ECG, BP, and pulse rate abnormalities from Day 1 up to Day 28 of potential clinical concern will be described. Safety data will be presented in tabular and/or graphical format and summarized descriptively, where appropriate, according to sponsor reporting standards.

For ECG data, the number of participants with uncorrected QT values >500 msec will be summarized. Listings of subjects with any single postdose value ≥500 msec will also be produced for QTcF. Numbers and percentages of subjects meeting the categorical criteria will be provided. All planned and unplanned measurements will be counted in these categorical summaries. All values meeting the criteria of potential clinical concern will be listed.

Seperate analysis for PT/INR, APTT, fibrinogen, ATIII activity and cTnI will include:

- Descriptive summary including n, mean, median, standard deviation, geometric mean, geometric coefficient of variation (geocv%), minimum, and maximum, will be reported from Day 1 up to Day 28.
- Listing of abnormalities.

Analysis change from baseline for PT/INR, APTT, fibrinogen, ATIII activity and cTnI will include:

• Descriptive summary including n, mean, median, standard deviation, minimum, and maximum, will be reported from Day 1 up to Day 28.

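### The SAP's TEAE rule tests only when an event starts, within an undefined period, so an AE that begins before the dose and worsens after it may be left out of the primary endpoint

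*SAP*

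**What the plan says.** The only rule for what makes an AE treatment-emergent is in SAP 3.5.1: it qualifies if "the event started during the effective duration of treatment regardless of whether a similar event of equal or greater severity existed" at baseline. The protocol uses the term in its endpoint table (Section 3) and expands the abbreviation in Appendix 9, but gives no definition.

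The other passages that bear on the point are:

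- **Endpoint.** The first primary endpoint in SAP 3.1 is "Frequency, severity and causal relationship of TEAEs and withdrawals due to TEAE; Day 1 up to Day 42".
- **Analysis.** SAP 6.1 plans "Analysis of frequency, severity and causal relationship of AEs, TEAEs from Day 1 up to Day 42".
- **Start of collection.** Under Protocol 8.3.1, active AE collection "begins from the time the participant provides informed consent". Screening may open up to 35 days before the dose (Protocol 4.1).
- **End of collection.** The same section continues collection "through and including a minimum of 42 calendar days after the last administration of the study intervention".
- **Updates to an AE.** Protocol 10.3.3 (follow-up of AEs and SAEs) says: "New or updated information will be recorded in the originally completed CRF".
- **Exacerbations.** Protocol 10.3.1 lists a flare of a chronic or intermittent condition, including greater frequency or intensity, among the events that meet the AE definition.

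**The concern.** A usual definition of treatment emergence has two limbs: a new event after the first dose, or an existing event that gets worse after it. SAP 3.5.1 has only the first. Its closing clause is generous to new events, since a similar or worse baseline event does not disqualify them, but it does nothing for an event whose recorded start is before the dose.

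The design makes such records possible. AEs are collected from consent, so some may be open when the participant is dosed. If one then worsens and the site updates the existing record, the start date stays before the dose.

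The start-only test also refers to a period, "effective duration of treatment", that has no evident meaning for a single injection and is not explained anywhere. The person programming the TEAE flag has to choose its start and end.

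Safety is the primary objective, and this flag decides what enters the frequency, severity and causality tables and the count of withdrawals due to TEAEs. An omitted post-dose worsening would make the drug look better tolerated than it was.

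**Working it through.** The plan states no figure to reproduce. The sample size of 6 has no statistical basis (Protocol 9.2) and there is no hypothesis test (SAP 5.1). The check is mainly a reading of the texts together.

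**Step 1: is the period defined?** The phrase occurs once, in SAP 3.5.1. It is absent from the protocol and from both abbreviation lists. SAP 3.1 and 6.1 give Day 1 to Day 42, but neither says that this is the period meant in 3.5.1.

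**Step 2: how is a worsening classified?** Take a hypothetical participant with a mild AE that starts in screening, is still open at dosing, and becomes moderate a few days after the injection.

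| How the site records it | Recorded start | TEAE under SAP 3.5.1? |
|---|---|---|
| Updates the original record (Protocol 10.3.3, follow-up) | Before the dose | No |
| Enters a new AE as an exacerbation (Protocol 10.3.1) | After the dose | Yes, despite the similar baseline event |

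The clinical course is the same and the primary endpoint differs. Neither document says which route applies to an AE already open at dosing. The only general instruction on later information points to the first row, although it does not mention severity or start dates.

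**Step 3: do the end dates agree?** With dosing on Day 1, Day N is N − 1 days after the dose.

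- Endpoint: Day 42, which is 41 days after the dose.
- Collection rule: at least 42 calendar days after the dose, which is Day 43.
- Day 42 visit window in the Schedule of Activities: ±7 days, so Day 35 to Day 49. A contact on Day 35 is 34 days after the dose, 42 − 34 = 8 days short of the collection minimum.

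A definition of the period has to settle this as well.

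**Step 4: scale.** One participant reclassified changes incidence by 1/6 = 16.7 percentage points. With exact (Clopper-Pearson) 95% intervals:

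- 0/6 = 0% (0 to 45.9%)
- 1/6 = 16.7% (0.4 to 64.1%)

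The documents give no probability p that a participant has a pre-dose AE that worsens after the dose. Taking p as an assumption, and participants as independent, the chance of at least one case among 6 is 1 − (1 − p)^6:

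| Assumed p | Chance of at least one case |
|---|---|
| 2% | 1 − 0.98^6 = 11% |
| 5% | 1 − 0.95^6 = 26% |
| 10% | 1 − 0.90^6 = 47% |
| 20% | 1 − 0.80^6 = 74% |

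These show how often the question could arise. They do not estimate a bias.

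**The case against.** The best defence is that the documents already allow the worsening to be counted. The protocol treats an exacerbation as an AE, and the SAP clause then includes it whatever existed at baseline. The sentence on updating the CRF may have been meant for outcome and follow-up details only. This stands in part: exclusion is possible, not certain. But the exacerbation bullet concerns chronic or intermittent pre-existing conditions, and does not say that an AE already open from screening is entered again with a new start.

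Second, SAP 6.1 names AEs as well as TEAEs, so an event without the flag may still be reported. That is fair, but it would not be in the TEAE count, which is the endpoint.

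Third, the sponsor's reporting standards, to which SAP 6.6 refers for AE summaries, may define the period. They may, but SAP 3.5.1 does not point to them for it.

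Fourth, the study is single-arm and descriptive, so no test or decision rule is affected. That limits the consequence, but with so few participants each classification is visible in the result.

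A reader might also infer that the undefined phrase cuts the window short, so that late events are lost. The documents do not support this. SAP 3.1 and 6.1 both state Day 1 to Day 42, and the SAP version history records a deliberate change of this endpoint from Day 28 to Day 42. Nor do they show that events before the injection on Day 1 would be counted: nothing says the period opens at the start of that calendar day, and a period of treatment would more naturally open with the dose.

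**Conclusion.** The point holds in a limited form. The treatment-emergence rule is start-only and rests on a period that is neither defined nor linked to the stated Day 1 to Day 42 window. A pre-dose AE that worsens after the injection may therefore be missing from the primary TEAE endpoint, depending on how the site records it.

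A reader might infer that every such event is lost. That goes too far, because a worsening entered as a new AE is counted.

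Each participant affected moves incidence by 16.7 points. How many would be affected is unknown. The conclusion assumes that the instruction on updating the original CRF record extends to a change in severity, which is a reasonable reading but is not stated. Any omission of this kind would lower the TEAE count. A severity criterion tied to the injection time would remove the dependence on site practice, so the change is worth making.

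**What to change.** 1. Replace the rule in SAP 3.5.1 with one along these lines: *a TEAE is any AE whose onset, or whose increase in severity, occurs at or after the time of the injection on Day 1 and no later than the end of the Day 42 follow-up.* Remove the undefined phrase.
2. State the end of that period as one rule, and reconcile the three places that now differ: Day 42 in the endpoint, at least 42 calendar days after the dose in Protocol 8.3.1, and the ±7-day window for the Day 42 visit.
3. Add a CRF completion instruction: when an AE that began before the dose worsens after it, the site either opens a new record or enters a dated severity change. Without that date, the new criterion cannot be programmed reliably.

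The cost is one SAP sentence, one CRF instruction and the reconciliation of dates. The TEAE count may be slightly higher. Because this settles how a primary endpoint is defined, the sponsor should also decide whether it needs a protocol amendment under the rule for major modifications in Protocol Section 9.
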